6.3 PACKAGING AND LABELING

Packaging and labeling will be prepared to meet regulatory requirements. For any sites located outside the United States, the package labeling will be translated into the local language.

The packaging/labeling on the PICO test article kit contain the following information:

- Name of Sponsor
- Study Number
- Expiry Date
- LOT Number
- “MUST be Stored at Room Temperature”
- **Exclusively for Clinical Evaluation Only**

6.4 TEST ARTICLE ACCOUNTABILITY PROCEDURES

The sponsor company (Smith & Nephew, Inc.) will keep a detailed record of all investigational product, ancillary product and study supplies/materials supplied to each site. Confirmation of receipt of the investigational product/ancillary product and any other study materials/supplies, by the Investigator will also be retained.

Study Supply Request forms will be provided for any additional products/materials needed to complete the study.

The receipt and dispensing of the study treatment will be recorded on appropriate accountability forms available for verification by the Sponsor or its designated representative at each

monitoring visit. Used investigational devices must not be discarded or destroyed by site staff. All used devices will be retained at room temperature in their original packages until checked by the study monitor, after which they will be released to the site for destruction or will be returned back to the Sponsor.

All investigational products will be clearly identified as per the labelling in section 6.3.

The Study Monitor will ensure that the procedures and records are in place for the appropriate reconciliation of all investigational products. As part of monitoring, the Study Monitor will check that the site personnel are following the procedures and completing all the necessary documentation.

6.5 CONCOMITANT THERAPY

Subjects will be instructed about care of their target ulcer area over the duration of the study.

Subjects are not allowed to use any topical lotions or ointments applied directly to the target ulcer, beneath the PICO or tNPWT wound dressing kits, as this may interfere with the delivery of topical Negative Pressure Wound Therapy to the target wound, and the ability of the wound dressing kits to obtain a good seal in the peri-wound area.

Antibiotics (oral or systemic) will be allowed if a subject develops an infection requiring treatment after being randomized into the study.

No chemotherapy, immunotherapy, systemic hormonal therapy (other than hormone replacement therapy, hormonal contraceptives, and inhaled steroids), radiation therapy, or experimental medications will be permitted while subjects are in the study.

With the exceptions noted above, any medications that are considered necessary for the subject's welfare that will not interfere with the study treatment may be given at the discretion of the Investigator. This includes any standard care for non-target ulcers deemed appropriate by the Investigator and not prohibited by this protocol. Administration of all concomitant medications must be documented, along with dates of administration and reasons for use.

Simultaneous participation in other clinical trials evaluating experimental treatments or procedures is not permitted.

7. SUBJECTS

7.1 SUBJECT POPULATION

A total of approximately 160 subjects, presenting with a lower extremity ulcer (VLU or DFU) will be recruited at approximately 15 investigational centers in the United States and Canada, but potentially including investigational centers located in the United Kingdom and European Union. Additional sites may be added, if necessary to meet recruitment goals. As a restriction within the total of 160 subjects, a minimum of 46 subjects presenting with a DFU will be recruited along with minimum of 100 subjects presenting with a VLU will be recruited, the remainder of recruitment will comprise of subjects with either ulcer type.

An interim analysis will be performed after 80 subjects have completed the study, including a minimum of 40 VLU and 20 DFU, at which point a recommendation may be to stop the study prematurely due to either efficacy or futility. The stopping criteria are detailed in the Statistical Analysis Plan (SAP).

7.2 INCLUSION CRITERIA

1. Provide informed consent, which will consist of reading, signing, and dating the informed consent document after the Investigator, sub-Investigator or other designated study staff member has explained the study procedures, risks, and contact information.
2. Age \geq 18 years, Male or Female.
3. Willing to comply with protocol instructions, including allowing all study assessments.

4. Women of child-bearing potential (those who are not premenarchal, not surgically sterilized [hysterectomy or bilateral oophorectomy], or not post-menopausal), may participate in the study if they meet all of following conditions:

- Not breast feeding
- A negative urine pregnancy test at screening
- Agree to undertake a urine pregnancy test upon exiting the study
- Do not intend to become pregnant during the study
- Using adequate birth control methods and agree to continue using those methods for the duration of the study

NOTE: Women who have had a bilateral tubal ligation are not considered to have been surgically sterilized and must agree to the conditions as specified above. Post-menopausal is defined as no menstrual period for at least one year.

5. Target ulcer involves a full thickness skin loss, but in the case of VLU, WITHOUT exposure of tendon, muscle, or bone.
6. Acceptable state of health and nutrition with pre-albumin levels of ≥ 10 mg/dL (0.10 g/L), serum albumin ≥ 2.0 g/dL (20 g/L), per the Screening central lab report, and no abnormal laboratory values that, in the opinion of the Principal Investigator, place the subject at risk for the trial.
7. An $HbA_{1C} < 12.0\%$ (108 mmol/mol) per the Screening central lab report.
8. Arterial supply adequacy confirmed by any one of the following:
- Systolic blood pressure Ankle Brachial Index (ABI) in the range $\geq 0.70 \leq 1.20$
 - Great toe pressure ≥ 40 mm/Hg
 - $TcPO_2 \geq 30$ mmHg from the foot
 - Normal triphasic or biphasic waveform pattern at the ankle
 - If ABI > 1.20 (**DFU subjects only**), perfusion at or near the site of the ulcer should be confirmed; the foot is warm to the touch and has palpable pulses.

9. **Subjects with a Venous Leg Ulcer (VLU):**

A. Should have an ulcer between the knee and ankle (at or above the malleolus), with a surface area $\geq 2.0 \text{ cm}^2$ and $\leq 36.0 \text{ cm}^2$ confirmed using the ARANZ Silhouette wound imaging and measurement device.

- If the subject presents with > 1 , but ≤ 3 venous leg ulcers on the same leg, the largest qualifying ulcer will be selected as the target ulcer.
- A true single target ulcer MUST be at least 2.0 cm from any other VLU and will be used for treatment and evaluation throughout the trial.

B. Target ulcer duration ≥ 4 weeks but ≤ 104 weeks (24 months).

C. The subject is suitable for multi-layer compression therapy and is willing to tolerate the synergistic use of NPWT and multi-layer compression bandages.

D. Documentation that subject has failed previous therapy (e.g., compression therapy).

10. **Subjects with a Diabetic Foot Ulcer (DFU):**

A. Should have an ulcer present on any part of the plantar or dorsum surface of the foot, with a surface area $\geq 0.5 \text{ cm}^2$ and $\leq 10.0 \text{ cm}^2$ confirmed using the ARANZ Silhouette wound imaging and measurement device.

- Separation of at least 5.0 cm (closest ulcer edge to other closest ulcer edge) if ≥ 2 ulcers are present.

B. Target ulcer duration ≥ 4 weeks but ≤ 52 weeks (12 months).

C. Diabetes mellitus (Type 1 or 2) requiring insulin or oral/injectable medications to control blood glucose levels.

7.3 EXCLUSION CRITERIA

1. Subjects with known allergies to product components (silicone adhesives and polyurethane films (direct contact with wound), acrylic adhesives (direct contact with skin), polyethylene fabrics and super-absorbent powders (polyacrylates) (within the dressing) or any contraindications with the use of NPWT (see Appendix 18.1).
2. Therapy with another investigational agent within thirty (30) days of Screening (Run-in Visit 1), or during the study.
3. Ulcers which are deemed as highly exuding, per the Investigator's discretion.
4. Current diagnosis of osteomyelitis at the target wound location that is not currently receiving treatment [Documented history of resolved osteomyelitis is allowed].
5. Malignancy in the target ulcer, or history of cancer in the preceding 5 years (other than carcinoma in situ of the cervix or adequately treated non-melanoma skin cancers).
6. Clinical evidence of target ulcer bed infection.
7. Current diagnosis of vasculitis or current diagnosis of claudication.
8. Current systemic therapy with cytotoxic drugs.
9. Current therapy with chronic (> 10 days) oral corticosteroids.
10. Previous treatment with NPWT device or hyperbaric oxygen within 7 days of screening.
11. Per Screening central lab hematology report, WBC < 2.0 x10⁹/L, neutrophils < 1.0 x10⁹/L, platelets < 100 x10⁹/L, and Hgb < 8.0 g/dL.
12. Per Screening central lab chemistry report, serum total bilirubin or serum creatinine ≥ 2 times the upper limit of the normal value (ULN); or, aspartate aminotransferase (AST), alanine aminotransferase (ALT) or alkaline phosphatase ≥ 3 times ULN.
13. The ulcer is in a location that is non-amendable to the creation of an airtight seal for the effective delivery of topical NPWT to the ulcer surface.

14. Subjects with a Venous Leg Ulcer (VLU):

- A. A target ulcer of non-venous etiology (e.g., sickle cell anemia, necrobiosis lipoidica diabetorum, pyoderma gangrenosum, vasculopathic or vasculitic).
- B. Deep Vein Thrombosis (DVT) that is acute, defined as the first 10 days from onset of symptoms, or any DVT for which compression bandaging is considered by the Investigator to be contraindicated.
- C. Refusal of or inability to tolerate compression therapy

15. Subjects with a Diabetic Foot Ulcer (DFU):

- A. Diagnosis of active Charcot foot syndrome
- B. Target wound location on toes

7.3.1 Additional Exclusion Criteria Prior to Randomization

Furthermore at the end of the run-in period, prior to randomization, the following exclusion criteria will apply for all subjects:

- 16. A reduction of the target ulcer area $\geq 30\%$ during the Run-in period.
- 17. Use of excluded concomitant medications, therapies, or procedures during the Run-in period.
- 18. A clinically diagnosed infection of the target ulcer requiring treatment.
- 19. Muscle, tendon, or bone exposure in the target ulcer (**VLU Subjects only**).
- 20. Severe uncontrolled edema of the target ulcer leg (**VLU Subjects only**).
- 21. The subject is not able to tolerate compression therapy as required by the protocol (**VLU Subjects only**).
- 22. The target ulcer is > 15 cm in one linear direction, confirmed by the ARANZ Silhouette wound imaging and measurement device (**VLU Subjects only**).
- 23. In the judgment of the Investigator, the subject is not an appropriate trial subject.

7.4 SCREENING LOG

Participating study sites are required to document all screened subjects initially considered for inclusion in this study. If a subject is excluded from the study, the reasons for exclusion will be documented in the subject's source documents and noted on the Screening Log.

8. STUDY DESIGN

8.1 STUDY DESIGN

This is a multi-center, Phase 4, randomized, open-labelled, comparative-effectiveness study in subjects with at least one lower extremity wound (VLU or DFU). Approximately 160 subjects, including a minimum of 100 subjects presenting with VLU and 46 presenting with DFU, will be randomized to one of two treatment groups in an equal allocation to receive either PICO single-use NPWT system or tNPWT system, for 12 weeks, or until target ulcer closure (by surgical intervention or secondary intention), whichever occurs first.

Subject randomization to trial treatment will be conducted using an online randomization system and will be stratified by the subject's ulcer type and ulcer size (cm²) at baseline. Each stratification factor will contain two levels: Venous Leg Ulcer or Diabetic Foot Ulcer, and Small or Large Ulcer with the definition of small and large dependent on ulcer type. The result will be four possible strata:

- Venous Leg Ulcer $\leq 12\text{cm}^2$ (small)
- Venous Leg Ulcer $> 12\text{cm}^2$ (large)
- Diabetic Foot Ulcer $\leq 2\text{cm}^2$ (small)
- Diabetic Foot Ulcer $> 2\text{cm}^2$ (large)

Further details regarding the randomization process will be provided in the SAP.

An interim analysis will be performed after 80 subjects have completed the study, incorporating a minimum of 40 VLU and 20 DFU.

CONFIDENTIAL DOCUMENT
This document contains confidential information, which is the property of Smith & Nephew, Inc. Do not copy, disclose, or circulate without written authorization from the appropriate Smith & Nephew personnel

8.2 METHODS USED TO MINIMIZE BIAS

The study is open-label due to visible differences in trial treatment devices. The use of random treatment allocation during the study will ensure that any selection bias (conscious or unconscious) on the part of the Investigator is avoided.

9. STUDY PROCEDURE

For a summary of the required procedures by visit, refer to Table 17-1: *Study Plan*.

9.1 VISITS AND EXAMINATIONS

9.1.1 Screening Run-in Visit 1

Assign a subject ID number to each subject who enters screening.

NOTE 1: Subjects who enter screening should have the potential heal, with excessive edema and infection under control.

NOTE 2: Any subject who signs an informed consent, but fails to meet the required entry criteria is considered to be a Screen Failure. Screen Failure subjects should have their demographic information captured with the reason for screen failure specified. Subjects may be re-screened 2 times. If a subject fails to meet all criteria after 3 screening attempts, the subject may not be enrolled into the study. A new informed consent is required for each screening attempt. All procedures, excluding the central lab, ABI, Toe Pressure, or TcPO₂ obtained within 30 days of re-screening, must be repeated for each screening attempt.

1. Explain the purpose and nature of the study, and have the subject or the subject's legally authorized representative **read, sign, and date** the IRB-approved informed consent document. Additionally, have the individual who obtains consent from the subject sign and date the informed consent document. Provide a photocopy of the signed informed consent document to the subject and place the original signed document in the subject's chart. Documentation of the informed consent process should be captured in each subject's source for each consenting.

----- Do not proceed until consent has been obtained -----

2. Screen the subject against the protocol inclusion and exclusion criteria for eligibility.
3. Obtain basic demographic information and relevant medical history, including information on all concomitant medications.
4. Complete a physical examination, body weight, height, and vital signs, including measurement of resting heart rate, respiratory rate, and blood pressure while seated.
5. Obtain complete history pertinent to the lower extremity target ulcer, including duration of the target ulcer, previous and current treatment and any other history that may have impacted the target ulcer (has it healed and re-occurred in the same location).
6. Assess target ulcer level of pain using the VAS.
7. Perform ulcer debridement if indicated. Debridement may only be performed using a curette, scissors, scalpel, or forceps.
8. Photograph and determine the post-debridement ulcer area (cm^2), perimeter (cm), greatest depth (mm), volume (cm^3) and maximum linear dimension (cm) using the ARANZ Silhouette wound imaging and measurement device.

If debridement is not performed, an image of the target ulcer is still required to determine the ulcer area (cm^2), perimeter (cm), greatest depth (mm), volume (cm^3) and maximum linear dimension (cm) using the ARANZ Silhouette wound imaging and measurement device.

9. Assess arterial supply adequacy of target limb by way of ABI. If ABI is out of range (> 1.20) or is not able to be performed at the investigational center, then an alternative test can be used to confirm arterial supply adequacy (e.g., Great Toe Pressure, TcPO₂, or normal triphasic or biphasic waveform pattern at the ankle). Additional options for DFU subjects are available to confirm arterial supply adequacy:
 - If ABI > 1.20 , perfusion at or near the site of the ulcer should be confirmed; the foot is warm to the touch and has palpable pulses.
10. Obtain blood samples for hematology, chemistry, serum pre-albumin and HbA_{1C} levels (send blood to central laboratory for analysis).

All females of child-bearing potential (including those who have had a bilateral tubal ligation) will undergo a urine pregnancy test and the results will be analyzed and documented by the site personnel.
11. Apply Iodoflex or Iodosorb as antimicrobial dressing plus ALLEVYN and PROFORE multi-layer compression bandaging (**For VLU subjects**).

Apply Iodoflex or Iodosorb as antimicrobial dressing and ALLEVYN Life (**For DFU subjects**).
12. If any adverse events in the target ulcer have occurred as a result of the screening or run-in procedures, the events must be reported and evaluated as instructed in Section 12, *Adverse Events*.
13. Subjects who do not meet eligibility will be screen failed and discharged, noting the reasons for disqualification.
14. Subjects who qualify to enter the run-in period will be instructed to refrain from using excluded medications and to return to the office for Screening Run-in Visit 2 within 7 (± 1) days.

9.1.2 Screening Run-in Visit 2 [± 1] Days After Screening Run-in Visit 1]

At Screening Run-in Visit 2 the following procedures will be performed prior to randomization, to assure that none of the exclusion criteria described in Section 7.3.1 are met. The Screening Run-in Visit 2 should occur at 7 (± 1) days after Screening Run-in Visit 1. The day on which this visit occurs will set the weekly visit day for all subsequent treatment Visits 2 through 12 if the subject is randomized. A (± 1) day visit window will be allowed. Subjects who do not return on the original day of the week for a scheduled visit at Study Visits 2-12 should be brought back on the original scheduled day at the subsequent visit. Subjects who do not meet all eligibility criteria will be considered screen failures and documented as such. Subjects who meet all entry criteria will complete the randomization procedure and this visit will then serve as Study Visit 1.

1. Subjects will be queried regarding any changes in general health and the use of concomitant medications.
2. If any adverse events in the target wound have occurred as a result of the screening or run-in procedures, since the last assessment, the events must be reported and evaluated as instructed in Section 12, *Adverse Events*.
3. Remove compression bandaging (**for VLU subjects**) and topical dressing (**both VLU/DFU subjects**) to assess the target ulcer.

Examine the ulcer for evidence of infection. If signs/symptoms indicate infection, remove the subject from the Run-in period as a screen failure.
4. Assess level of pain, post dressing removal, using the VAS.
5. Debride the ulcer if indicated, at the discretion of the Investigator.

After debridement if presence of necrotic tissue or eschar within the target ulcer, subject should be screen failed.
6. Photograph and determine the post-debridement ulcer area (cm²), perimeter (cm), greatest depth (mm), volume (cm³) and maximum linear dimension (cm) using the ARANZ Silhouette wound imaging and measurement device. This is the baseline

CONFIDENTIAL DOCUMENT
This document contains confidential information, which is the property of Smith & Nephew, Inc. Do not copy, disclose, or circulate without written authorization from the appropriate Smith & Nephew personnel

ulcer assessment measurement.

If debridement is not performed, an image of the target ulcer is still required to determine the ulcer area (cm²), perimeter (cm), greatest depth (mm), volume (cm³) and maximum linear dimension (cm) using the ARANZ Silhouette wound imaging and measurement device. This is the baseline ulcer assessment measurement.

Calculate the percent change in ulcer area.

$$\Delta = \frac{Area_{RV2} - Area_{RV1}}{Area_{RV1}} \times 100\%$$

If (Δ) percent change \geq 30% decrease in target ulcer area; subject will be excluded from randomization and participation in the study.

9.1.3 Randomization Study Visit 1

This visit is a continuation of Screening Run-in Visit 2 for all eligible subjects and should be completed on the same day.

Upon completion of all Screening Run-in Visit 2 procedures and confirmation that the subject is eligible for the study, the Investigator or designee will register the subject using an electronic randomization system to calculate the percent change in the target ulcer. If the subject's percent change meets the eligibility criteria the subject will be randomized and then will enroll into the treatment period of the study. The randomization will be stratified based on target ulcer size and wound type observed at the screening visit. The details of the stratification factors and the process of the stratified randomization will be provided in the SAP. The subject will then receive the study treatment allocated to that subject identification number per instructions received from the electronic randomization system. Then the following procedures will be completed:

1. Subjects will be randomized using an electronic randomization system (www.sealedenvelope.com) to either treatment with PICO or tNPWT systems, and assigned a subject randomization number.
2. Conduct an ulcer assessment using the modified Bates-Jensen wound assessment

CONFIDENTIAL DOCUMENT
This document contains confidential information, which is the property of Smith & Nephew, Inc. Do not copy, disclose, or circulate without written authorization from the appropriate Smith & Nephew personnel

tool and record percentage tissue type/condition of peri-wound skin assessment (Normal, Erythematous, Edematous, Eczematous, Excoriated, Macerated, Indurated).

3. Ask the subject to complete the Cardiff Wound Impact Schedule (CWIS) quality of life questionnaire and EQ-5D.
4. Application of investigational product (PICO) or comparator tNPWT system according to randomization schedule.

Record any additional dressings used and rationale for using this dressing.

Type of wound filler dressing if used (foam or gauze-based filler dressing).

Number of personnel used to apply NPWT system.

Time used to apply NPWT system (minutes).

Record level of negative pressure, intensity setting and delivery mode selected for tNPWT subjects, if appropriate for device selected.

Apply Profore compression bandage over the NPWT dressing for VLU subjects only.

5. Record subject's level of pain, during initiation of NPWT therapy, using VAS.
6. Subjects will be instructed to refrain from using excluded medications, and to return to the office for Study Visit 2 in 7 (\pm 1) days.

Subjects using a negative pressure filler dressing will be instructed to complete a dressing change in 2-3 days from application.

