9.1.4 Study Visits 2-12

The treatment period is defined as Randomization Study Visit 1 through Study Visit 12. During the study treatment period, any AE associated with the target ulcer and all SAE of any kind will be recorded in the appropriate eCRF. Device deficiencies (DevD) will be recorded in a separate eCRF. The evaluation of all AE is described in Section 12, *Adverse Events*. All weekly visits

must be performed according to the study visit schedule (Section 17), preferably on the same day each week, to conduct all assessments and to assure compliance with treatment. A plus or minus one day visit window will be used for all study visits.

VLU subjects found to have target ulcer closure should continue the compression dressing. Appropriate treatment for DFU subjects found to have target ulcer closure is left to the Investigator's discretion. Appropriate treatment for VLU and DFU subjects, whose target ulcer is ready for and will be surgically closed, is left to the Investigator's discretion. If the Investigator believes the target ulcer is ready for surgical closure, then this procedure should be completed within the same week of the scheduled study visit. The next scheduled visit for subjects with closed target ulcers or subjects that will be surgically closed will be designated as End of Treatment Assessment Visit 14 and should occur in 7 (± 1) days.

All study procedures should occur in the order outlined in the protocol. Study Visits occurring outside the protocol specified visit window should be completed and recorded as a protocol deviation.

1. Subjects will be queried regarding any changes in general health and the use of concomitant medications.
2. Any AE associated with the target ulcer and all SAE of any kind reported since the last assessment will be recorded in the appropriate eCRF. DevD will be recorded in a separate eCRF (see "Section 12, *Adverse Events*" for reporting and evaluating AE). Also, subjects will be queried as to any additional ulcer-related interventions requiring hospital admission, surgical intervention or specialist referral since the last assessment.
3. Assess level of pain from NPWT dressing wear, since the previous study visit, using the VAS.
4. Prior to examination of the ulcer, remove compression bandaging (**for VLU subjects**) and photograph the NPWT topical dressing using the ARANZ Silhouette wound imaging and measurement device.

CONFIDENTIAL DOCUMENT

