3.2 RANDOMIZATION

All eligible subjects will be randomized between PICO and ActiV.A.C.[®] therapy settings by means of an online randomisation system (Sealed Envelope).

Treatment will be randomized, stratified by wound type and wound size at the conclusion of the screening period (and prior to commencement of the treatment period) to prevent imbalance on these variables between the two treatment groups.

The resulting strata will be as follows:

- *Small DFU ($\leq 2 \text{ cm}^2$)*
- *Large DFU ($> 2 \text{ cm}^2$)*
- *Small VLU ($\leq 12 \text{ cm}^2$)*

- Large VLU (>12 cm²)

A blocked randomization will be used for each stratum utilizing a block size of 2 and 4. Due to visible differences between treatments, allocation to treatment will not be blinded.

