4.9 Primary Variable

The primary objective of the study is to compare PICO against ActiV.A.C.® in terms of the percentage change in the target ulcer area, over the 12-week treatment period.

Primary Analysis

An initial linear regression model will contain covariates for treatment, center, wound type, baseline (defined as Run-In Visit 2/Study Visit 1) target ulcer area and duration of target ulcer. For purposes of the primary analysis, any centers with less than 10 subjects will be pooled. A forward selection procedure will be used for the addition of other baseline covariates with an F-value to attain a significance level of 0.1. Further baseline covariates to be assessed as part of this procedure include: subject age, body mass index, baseline ulcer depth, ABI and baseline level of exudate. The resulting primary analysis presented will correspond to the final model from the forward selection procedure. The results for the initial model will also be presented. For each of the effects in the initial and final model, the p-value, parameter estimate and corresponding 95.4% confidence interval will be presented.

Non-inferiority will be concluded if the upper bound of the 95.4% confidence interval for the parameter estimate relating to treatment covariate (coded as ActiV.A.C.® – PICO) is less than ($<$) 12.5 which relates to the desired one-sided test at the 2.5% significance level after adjusting for the interim analysis.

If distributional and model assumptions relating to the above analysis do not hold, a permutation test will be used as a non-parametric non-inferiority analysis. The sampling distribution of the test statistic will be estimated by re-randomization of treatments to each of the study subjects. At a minimum the completed re-randomization process will be repeated 2000 times. However, if 2000 replicates are found to be insufficient for the random variation in results of successive repeats to be reduced to an acceptable level, the number of replicates will be increased until such a point as consistent results are observed between successive repeats of the permutation tests up to a maximum of 10,000 replicates.

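### Baseline CWIS, EQ-5D and Bates-Jensen assessments come after randomization in an open-label trial, so knowledge of the arm can shift the quality-of-life baselines

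*Protocol*

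**What the plan says.** Protocol 9.1.3 (Randomization Study Visit 1) numbers its steps:

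- Step 1 is the allocation: "Subjects will be randomized using an electronic randomization system".
- Step 2 is the wound grading: "Conduct an ulcer assessment using the modified Bates-Jensen wound assessment". Peri-wound skin is recorded at the same step.
- Step 3 brings in the questionnaires: "Ask the subject to complete the Cardiff Wound Impact Schedule (CWIS) quality of life questionnaire and EQ-5D".
- At step 4, and not before, the allocated device is fitted.

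Protocol 9.1.4 adds: "All study procedures should occur in the order outlined in the protocol". That sentence stands under Study Visits 2-12 but is worded for study procedures in general.

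Screening Run-in Visit 2 (protocol 9.1.2) takes place earlier on the same day and before randomization. It includes pain VAS, an infection check, debridement if indicated, the ARANZ measurement and the area-change check. It does not include CWIS, EQ-5D or Bates-Jensen. Table 17-1, in the protocol and in SAP 2.2, first marks the questionnaires and the target-ulcer assessment at Study Visit 1.

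On blinding, protocol 8.2 says "The study is open-label due to visible differences in trial treatment devices" and names random allocation as the only bias control. SAP 3.2 says "allocation to treatment will not be blinded".

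**The concern.** A baseline should be fixed before anyone can react to the allocation. Here the subject may answer the questionnaires, and the investigator may grade the wound, already knowing which device will be fitted a few minutes later. Randomization balances what existed before it and cannot protect a measurement taken after it.

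A route for such a reaction is easy to see. Protocol 4.3 describes the canister system as intrusive and PICO as easier to live with, and the study sets out to look for a quality-of-life benefit from the smaller device. Healing confidence, wound-related frustration and self-rated health today could all move on hearing the allocation. At stake is a named secondary objective (HRQoL): a baseline shift could create a false difference or hide a real one.

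The exudate grade offers a second route. Protocol 6.2 ties PICO's intended use and kit life to exudate level, so an assessor who knows the arm grades exudate in an arm-specific context.

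**Working it through.** **1. Is there a pre-allocation baseline?** Setting protocol 9.1.2, 9.1.3 and Table 17-1 side by side, there is none for CWIS, EQ-5D or Bates-Jensen. Area, depth and volume do have one, at Run-in Visit 2.

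**2. Does the analysis absorb a shift?** Protocol 9.4 defines change as end of treatment minus Study Visit 1. SAP 4.3 (derived variables 23 and 25) reverses the subtraction. SAP 4.10 tests change with a two-sample t-test, or a Wilcoxon rank-sum test if assumptions fail. Protocol 10.3.2 uses a Wilcoxon test stratified by wound strata. None includes the baseline score.

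Let θ be the true difference in change (PICO minus tNPWT) and d the shift in the PICO baseline relative to the tNPWT baseline caused by knowing the arm. With end-of-treatment answers unchanged:

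- protocol convention: expected difference = θ − d
- SAP convention: expected difference = −θ + d

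The shift enters in full either way. The direction of d is not known.

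**3. The plan's own figure.** The plan gives no SD, effect or power for HRQoL. Its only sample-size figure is for the primary endpoint: 128 subjects for 80% power, margin 12.5, SD 24.5, one-sided 0.025. A two-look calculation with 64 per arm, bounds Z = 2.963 and Z = 0.559 and half the information at the interim gives 80.2%, which reproduces it. Then 128 / (1 − 0.20) = 160. These numbers are used below only for n per arm (64 or 80).

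**4. Scale of the effect on the HRQoL tests.** Let b be the shift in units of the SD of the change score (assumed), with θ = 0 and a two-sided 5% test:

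rejection rate = Φ(−1.96 + b/√(2/n)) + Φ(−1.96 − b/√(2/n))

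Example: n = 64, b = 0.2. √(2/64) = 0.1768 and 0.2/0.1768 = 1.131, so Φ(−0.829) + Φ(−3.091) ≈ 0.205.

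| b (assumed) | 64 per arm | 80 per arm |
|---|---|---|
| 0 | 5.0% | 5.0% |
| 0.1 | 8.7% | 9.7% |
| 0.2 | 20.5% | 24.4% |
| 0.3 | 39.6% | 47.5% |

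**5. Would adjusting for baseline be enough?** Take a shift of 0.2 SD of a single measurement, correlation 0.5 between baseline and end of treatment (both assumed) and 64 per arm. The change score has bias 0.2 and SD √(2(1 − 0.5)) = 1, giving 20.5%. ANCOVA has bias 0.5 × 0.2 = 0.1 and SD √(1 − 0.5²) = 0.866, giving 10.0%. Adjustment reduces the error but does not remove it.

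**6. Where does exudate enter?** It is a fixed term in the exploratory wear-time model (protocol 10.3.3, SAP 4.11). For the primary model, SAP 4.9 lists it among forward-selection candidates: "subject age, body mass index, baseline ulcer depth, ABI and baseline level of exudate", with entry at 0.1. The closure and time-to-closure models treat it the same way.

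**The case against.** Several points on the other side stand.

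- **The subject may not know the arm.** A reader might infer that every subject has been told by step 3. The protocol does not say so. It says only that the investigator or a designee operates the system and that the device is applied at step 4. Nothing withholds the arm either, so this is an opportunity for bias and not an established event.
- **Much of CWIS looks back.** The 12 + 7 = 19 experience items ask about the past week, and the 19 paired stress items refer to those experiences. At this visit that week is the run-in, before any NPWT. Of the 24 + 14 + 7 = 45 domain items, the 7 well-being items carry no recall period. These and the EQ-5D, which asks about today, are the more exposed.
- **The primary analysis is largely clear of this.** A reader might infer that the primary endpoint is compromised. Its baseline area is measured before randomization, as are depth and volume. Exudate enters the primary model only if selected, and biasing the treatment estimate would need both an arm-related grading shift and a non-zero exudate coefficient. The initial model (without exudate) and a treatment-only model are also reported.
- **Some checks exist.** SAP 4.8 tests baseline exudate between arms, SAP 4.10 summarizes baseline CWIS and EQ-5D, and highly exuding ulcers are excluded before randomization. These may reveal a shift, but they cannot separate it from chance imbalance or undo it.
- **End-of-treatment answers stay open-label.** Re-ordering cannot change that. It is no reason to leave the avoidable part in place.
- **The order clause sits in 9.1.4.** Applying it to 9.1.3 is an inference, but the numbered list in 9.1.3 gives the same order by itself.

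**Conclusion.** The point holds as a sequencing weakness in the HRQoL baselines, and more narrowly in the Bates-Jensen exudate grade. All randomized subjects, about 160, are potentially exposed. Any shift caused by knowing the arm carries in full into the change-score comparison, but the documents give no basis for its size or direction. The rejection rates above are therefore illustrations. They assume a normal approximation, no true effect, unaffected end-of-treatment answers and items answered on both occasions (SAP 2.3.5 carries single missing end-of-treatment items forward from baseline, where a shift would cancel).

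The documents do not support a claim that bias has occurred, that exudate is a fixed term in the primary model, or that the area, depth or volume baselines are affected. The change is worth making because the route is avoidable at almost no cost and bears on a named secondary objective.

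**What to change.** In protocol 9.1.2 and 9.1.3, move the modified Bates-Jensen and peri-wound assessment, the CWIS and the EQ-5D to the end of Screening Run-in Visit 2, after the area-change check and before the subject is randomized. Mark all three as pre-randomization in Table 17-1 in both documents, and align the text of SAP 2.2. Device application stays after randomization. While editing, reconcile the sign of HRQoL change between protocol 9.4 and SAP 4.3.

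The cost is a re-ordering within one visit day, with no added visit. A few subjects may complete the questionnaires and then not be randomized. N stays at 128 completers and 160 randomized. Knowledge of the arm could then no longer shift these baselines; open-label reporting at end of treatment remains and should be acknowledged when the HRQoL results are interpreted.
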